4.2.3.3 Mixed models repeated measures of change from baseline in PRO symptoms

In addition to the time to deterioration endpoints listed above the following longitudinal endpoints are of interest: EORTC QLQ-C30 global health status, physical functioning, fatigue and appetite loss; LC13 dyspnoea, cough and chest pain. These are not part of the main multiple testing procedure and are considered a separate set of PRO endpoints from the time to deterioration endpoints listed above. A Bonferroni adjustment to the significance level will be applied to the tests described below to control the overall Type I error at the 5% level.

Change from baseline in these pre-specified the PRO symptom scores of dyspnea, cough, chest pain, fatigue and appetite loss, global health status and physical functioning will be analysed using a mixed model for repeated measures (MMRM) analysis making use of all data from baseline up to 12 months. The analysis will be to compare the average treatment effect from the point of randomisation until PD or 12 months (whichever is earlier) unless there is excessive missing data (defined as >75% missing data). It is acknowledged that patients will discontinue treatment at different timepoints during the study and that this is an important time with regards to symptoms and HRQoL data collection. To account for this, and in order to include the discontinuation and follow up visits, a generic visit variable will be derived for each subject in order that the average treatment effect can be analyzed using the above method. Each visit will be assigned a sequential number. The time from randomization

to each of these will be derived in order to select only those visits occurring within the first 12 months of randomization or until PD.

As an example, say a patient X attends the first 4 scheduled visits of a 4-weekly schedule and then discontinues treatment, whilst patient Y discontinues treatment after the first scheduled visit, the first 6 generic visits would be as follows:

Generic visit	Study Day	
	Patient X	Patient Y
Baseline	Baseline	Baseline
1	29	28
2	57	50 (discontinuation)
3	85	85
4	113	113
5	130 (discontinuation)	141
6	169	169

The MMRM model will include the fixed, categorical effects of treatment, visit, and treatment-by-visit interaction, age at randomisation (<65 vs ≥65 years of age), sex (male vs female), smoking history (smoker vs non-smoker as well as the continuous fixed covariate of baseline score and the baseline score-by-visit interaction). Restricted maximum likelihood (REML) estimation will be used. An overall adjusted mean estimate will be derived that will estimate the average treatment effect over visits giving each visit equal weight. For this overall treatment comparison, adjusted mean estimates per treatment group and corresponding 95% CIs will be presented along with an estimate of the treatment difference, 95% CI and p-value

An unstructured covariance matrix will be used to model the within-subject error and the Kenward-Roger approximation will be used to estimate the degrees of freedom. If the fit of the unstructured covariance structure fails to converge, the following covariance structures will be tried in order until convergence is reached: toeplitz with heterogeneity, autoregressive with heterogeneity, toeplitz, autoregressive and compound symmetry.

Multiple imputation techniques for missing values may be considered to explore the robustness of any treatment effect.

An effect size estimate to interpret the magnitude of the effect and potential therapeutic benefit will be further specified in the PAP.

4.2.4 Safety data

Safety and tolerability data will be presented by treatment arm using the safety population. Safety summaries will be descriptive only. No formal statistical analyses will be performed on the safety variables.

Any safety summaries examining re-treatment of study medication will be produced separately as needed.

The following sections describe the planned safety summaries for AEs, vital signs, laboratory parameters, ECG and WHO performance status. However, additional safety summaries (not specified in this SAP) may need to be produced to aid interpretation of the safety data.

4.2.4.1 Adverse events

All AEs, both in terms of current MedDRA preferred term and CTCAE grade, will be summarised descriptively by count (n) and percentage (%) for each treatment group. Any AE occurring before randomized treatment (i.e. before the administration of the first infusion on Study Day 1) will be included in the AE listings, but will not be included in the summary tables (unless otherwise stated). These will be referred to as 'pre-treatment'.

AEs observed up until 90 days following discontinuation of the study treatment (i.e., the last dose of randomised treatment) or until the initiation of the first subsequent anti-cancer therapy (including radiotherapy, with the exception of palliative radiotherapy) following discontinuation of study treatment (whichever occurs first) will be used for reporting of all of the AE summary tables. This will more accurately depict AEs attributable to study treatment only as a number of AEs up to 90 days following discontinuation of the study treatment are likely to be attributable to subsequent therapy.

However, to assess the longer term toxicity profile, all of the AE summaries will also be produced containing AEs observed up until 90 days following discontinuation of the study treatment (ie without taking subsequent therapy into account).

All reported AEs will be listed along with the date of onset, date of resolution (if AE is resolved) and investigator's assessment of severity and relationship to study drug. Frequencies and percentages of patients reporting each preferred term will be presented (i.e. multiple events per patient will not be accounted for apart from on the episode level summaries).

Summary information (the number and percent of patients by system organ class (SOC) and PT separated by treatment group) will be tabulated for:

- All AEs
- All AEs causally related to study medication (as determined by the reporting investigator)

- AEs with CTCAE grade 3 or higher
- AEs with CTCAE grade 3 or higher, causally related to study medication (as determined by the reporting investigator)
- Most common AEs
- Most common AEs with CTCAE grade 3 or higher
- AEs with outcome of death
- AEs with outcome of death causally related to study medication (as determined by the reporting investigator)
- All SAEs
- All SAEs causally related to study medication (as determined by the reporting investigator)
- AEs leading to discontinuation of study medication
- AEs leading to discontinuation of study medication, causally related to study medication (as determined by the reporting investigator)
- AEs leading to dose interruption of study medication
- Other significant AEs
- Immune mediated AEs (as determined by the reporting investigator)
- Infusion reaction AEs (as determined by the reporting investigator)

An overall summary of the number and percentage of patients in each category will be presented, as will an overall summary of the number of episodes in each category. In addition, a truncated AE table of most common AEs and another table showing most common AEs with CTCAE grade 3 or higher, showing all events that occur in at least 5% of patients overall will be summarised by preferred term, by decreasing frequency in the total column (although the total column may not be displayed in the AE tables). This cut-off may be modified after review of the data. When applying a cut-off (i.e., x %), the raw percentage should be compared to the cut-off, no rounding should be applied first (i.e., an AE with frequency of 4.9% will not appear if a cut-off is 5%). Summary statistics showing the time to onset and the duration of the first AE may also be presented as appropriate.

Each AE event rate (per 100 patient years) will also be summarised by preferred term within each SOC for the output summarising all AEs. For each preferred term, the event rate is defined as the number of patients with that AE divided by the total drug exposure of patients

at risk of AE divided by the total drug exposure of patients and then multiplied by 365.25 x 100 to present in terms of per 100 patient years.

Summaries of the number and percentage of patients will be provided by maximum reported CTCAE grade, SOC, PT and treatment group.

Fluctuations observed in CTCAE grades during study will be listed for those AEs which are CTCAE ≥ 3 .

In addition, all AEs will be listed.

Deaths

Two summaries of all deaths will be provided with number and percentage of patients by treatment group, categorised as:

- Total number of deaths (regardless of date of death)
- Related to disease under investigation only
- AE outcome of death only and onset date prior to initiation of subsequent anti-cancer therapy
- AE outcome of death only and onset date falling after 90 days following last dose of study medication or initiation of subsequent anti-cancer therapy (whichever is earlier)
- Both related to disease under investigation and with AE outcome=death and onset date prior to initiation of subsequent anti-cancer therapy
- Death related to disease under investigation and AE with outcome=death > 90 days after last dose of study medication or \geq date of subsequent therapy, whichever occurs first
- Deaths > 90 days after last dose of study medication or \geq date of subsequent therapy (whichever occurs first), unrelated to AE or disease under investigation
- Patients with unknown reason for death.
- Other deaths

This summary will be repeated for all deaths within 90 days of last dose of study medication.

Adverse events of special interest

PTs used to identify adverse events of special interest (AESI), as defined in Section 3.4.1, will be listed before DBL and documented in the Study Master File.

Grouped summary tables of certain MedDRA PTs will be produced. For each ‘grouped’ term, the number (%) of patients experiencing any of the specified terms will be presented by maximum CTCAE grade. Additional summaries will include Time to Onset of first CTCAE grade 3 or higher. Time to onset of first AE for each grouped term and preferred term within it will also be produced. Groupings will be based on preferred terms provided by the medical team prior to DBL, and a listing of the preferred terms in each grouping will be provided.

Additional summaries of the above-mentioned grouped AE categories will include number (%) of patients who have:

- At least one AESI presented by outcome
- At least one AESI causally related to study medication
- At least one AESI leading to discontinuation of study medication

A summary of total duration (days) of selected AESI will be provided. Additional information to be summarised will include number of patients with an event (n %), number of episodes of event (n), median total duration of event (days, range) and median duration of CTCAE grades 1, 2, 3, 4 (days, range).

Additionally, there will be several summaries of AESIs requiring concomitant treatment, and particularly the relationship of AESIs to the use of immunosuppressive agents (ie, depicting which AESI triggered immunosuppressive use) and, separately, to the use of immunosuppressive agents at high doses.”

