## **Radiation pneumonitis**

Symptoms of radiation pneumonitis, including low-grade fever, congestion, dry cough, pleuritic chest pain, and a sensation of chest fullness, usually develop 1 to 3 months after completion of radiation therapy. Diagnosis is difficult, often complicated by co-morbid conditions and radiation injury to adjacent structures (eg, oesophagus, pericardium). Prednisone, in dosages of at least 50 to 60 mg per day for 1 week followed by an extended taper, has been shown to abate symptoms and improve lung function. Bronchodilators and supplemental oxygen may be necessary.

More specific guidelines for the evaluation and treatment of pneumonitis are described in detail in the TMGs.

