### **Variables**

The following variables will be collected for each AE on the eCRF:

- AE (verbatim)
- The date and time when the AE started and stopped
- The maximum CTCAE grade reported
- Whether the AE is serious or not
- Investigator causality rating against the investigational product (yes or no)
- Action taken with regard to investigational product
- Administration of treatment for the AE
- AE caused patient's withdrawal from study (yes or no)
- Outcome.

In addition, the following variables will be collected for SAEs:

- Date AE met criteria for SAE
- Date Investigator became aware of SAE
- AE is serious due to
- Date of hospitalisation
- Date of discharge
- Probable cause of death
- Date of death

- Autopsy performed
- Causality assessment in relation to Study procedure(s)
- Causality assessment in relation to Other medication
- Description of AE.

It is important to distinguish between serious and severe AEs. Severity is a measure of intensity whereas seriousness is defined by the criteria in Section 6.4.2. An AE of severe intensity need not necessarily be considered serious. For example, nausea that persists for several hours may be considered severe nausea, but not a SAE. On the other hand, a stroke that results in only a limited degree of disability may be considered a mild stroke but would be a SAE.

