## **11.2 Calculation or derivation of safety variable(s)**

### **11.2.1 Adverse events**

Data from all cycles of randomised treatment will be combined in the presentation of safety data. AEs (both in terms of MedDRA preferred terms and CTCAE grade) will be listed individually by patient and treatment arm.

Any AE occurring before treatment with study drug will be included in the data listings but will not be included in the summary tables of AEs.

Any AE occurring within 90 days of discontinuation of investigational product (ie, the last dose of MEDI4736 or placebo) may be included in the AE summaries, but the majority of those summaries will omit those AEs observed after a patient has received further therapy for cancer. Further details will be provided in the SAP. Any events in this period that occur after a patient has received further therapy for cancer (following discontinuation of study drug) will be flagged in the data listings.

A separate data listing of AEs occurring more than 90 days after discontinuation of study drug will be produced. These events will not be included in AE summaries.

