3.4.1 Adverse events

AEs and SAEs will be collected throughout the study, from date of informed consent to 90 days after the last dose of MEDI4736 or placebo. The Medical Dictionary for Regulatory Activities (MedDRA) will be used to code the AEs. AEs will be graded according to the National Cancer Institute Common Terminology Criteria for AEs (CTCAE Version 4.03). A treatment emergent adverse event (TEAE) is an AE with an onset date or a pre-existing AE worsening following the first dose of study treatment through to 90 days after the last dose of MEDI4736 or placebo.

Adverse events that have missing causality (after data querying) will be assumed to be related to study drug.

Other significant adverse events

During the evaluation of the AE data, an AstraZeneca medically qualified expert will review the list of AEs that were not reported as SAEs and ‘Discontinuation of Investigational Product due to Adverse Events’ (DAEs). Based on the expert’s judgment, significant adverse events of particular clinical importance may, after consultation with the Global Patient Safety Physician, be considered other significant adverse events (OAEs) and reported as such in the CSR. A similar review of laboratory/vital signs/ECG data will be performed for identification of OAEs.

Examples of these are marked haematological and other laboratory abnormalities, and certain events that lead to intervention (other than those already classified as serious) or significant additional treatment.

AEs of special interest

Some clinical concepts (including some selected individual preferred terms [PTs] and higher level terms [HLTs]) have been considered “AEs of special interest” (AESI) to the MEDI4736

program. AEs represent pre-specified risks which are considered to be of importance to a clinical development program.

These AEs identified as a list of categories provided by the clinical team. Other categories may be added as necessary or existing terms may be merged. An AstraZeneca medically qualified expert, after consultation with the Global Patient Safety Physician, has reviewed the AEs of interest and identified which preferred terms contribute to each AE. A further review will take place prior to DBL to ensure any further terms not already included are captured within the categories.

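### The SAP's rule for building the AE tables does not apply its own treatment-emergent definition, so an AE that starts before the first infusion and worsens on treatment can be left out of the tables

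*SAP*

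**What the plan says.** SAP 3.4.1 collects AEs "from date of informed consent to 90 days after the last dose of MEDI4736 or placebo", so an AE can be on record before any study drug is given. It then defines a treatment-emergent AE as "an AE with an onset date or a pre-existing AE worsening following the first dose of study treatment", up to 90 days after the last dose.

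SAP 4.2.4.1 specifies the tables. Its rule for the start of the reporting window covers "Any AE occurring before randomized treatment (i.e. before the administration of the first infusion on Study Day 1"). The consequence for each of these events is that it "will be included in the AE listings, but will not be included in the summary tables (unless otherwise stated"). Such events are labelled pre-treatment. The tables that follow (all AEs, Grade 3 or higher, fatal outcome, serious, AESI by maximum grade) are described as tables of AEs. The treatment-emergent term does not appear among them.

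Protocol 11.2.1 treats AEs before study drug the same way: they go in the listings "but will not be included in the summary tables of AEs", with no provision for later worsening.

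Protocol 6.4.3 (Variables) lists what the eCRF holds for each AE. This includes start and stop date and time, and "The maximum CTCAE grade reported".

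**The concern.** A definition has been written and is then not used where it would decide something. One programmer, working from 3.4.1, would tabulate an AE that began before dosing and worsened afterwards. Another, working from 4.2.4.1, would put the same AE in the listings only. They would report different counts from the same data.

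The design makes such events plausible. Screening spans up to 42 days (protocol Table 1), soon after thoracic chemoradiation. Exclusion criteria 11 and 12 allow entry with pneumonitis below Grade 2 and with other unresolved toxicity up to Grade 2. Pneumonitis is an AESI (protocol 5.5.3.1). Worsening on treatment of an injury that began before treatment is something a comparison of arms should show, and that comparison is read from the summary tables, not the listings.

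**Working it through.** The plan states no figure on this point, so there is none to reproduce. The check is a comparison of texts, followed by a bound on the pneumonitis route.

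**1. One event under each rule.** Take an AE that starts at Grade 1 between consent and first infusion and reaches Grade 3 on treatment.

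| How it is recorded | SAP 3.4.1 | SAP 4.2.4.1, read literally | Protocol 11.2.1 |
|---|---|---|---|
| One record, start date before dosing | Treatment-emergent (worsened after first dose) | Listed, not tabulated | Listed, not tabulated |
| Worsening entered as a new AE | Treatment-emergent (onset after first dose) | Tabulated | Tabulated |

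The rules differ only in the first row. No text tells sites which row applies.

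**2. Is within-event grade change available?** The variables in protocol 6.4.3 are one start and stop date and one maximum grade per AE. SAP 4.2.4.1, however, plans a listing of grade fluctuations for AEs of Grade 3 or higher, and for AESIs a summary of duration at each of Grades 1 to 4 and of time to first Grade 3 or higher. Those outputs need dated grade changes within an event. This makes single-record entry plausible, and it means a date of worsening should be obtainable.

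**3. Which outputs are affected.** Affected in the first row: the all-AE, Grade 3 or higher, AE-with-outcome-of-death and AESI tables. Not affected: the AE listings, the listing of grade fluctuations, and the separate deaths summary, which counts all deaths and sets no first-dose lower limit on the onset of a fatal AE.

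**4. How far pneumonitis can be affected.** Inputs:
- radiation pneumonitis symptoms "usually develop 1 to 3 months after completion of radiation therapy" (protocol 5.5.3.1), taken as days 30 to 90 (assumption: 30-day months);
- randomisation 1 to 42 days after radiation (SAP 1.2), with dosing within 24 hours of randomisation (notes to protocol Table 1);
- rate 5% to 15% (protocol 5.5.3.1, for breast, lung and mediastinal irradiation together);
- arms: 702 × 2/3 = 468 and 702 × 1/3 = 234.

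Assume onset is uniform over the window (not in the documents). The share of onsets before the first dose is then:
- dosed by day 30: 0;
- dosed at day 42: (42 − 30)/(90 − 30) = 12/60 = 0.20. Taking day 43 and a window ending at day 91 gives 13/61 = 0.21.

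If every patient were dosed at day 42, onsets before dosing would number:
- MEDI4736: 468 × 0.05 × 0.20 = 4.7, to 468 × 0.15 × 0.20 = 14.0;
- placebo: 234 × 0.05 × 0.20 = 2.3, to 234 × 0.15 × 0.20 = 7.0.

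These are ceilings on onsets before dosing under the stated assumptions, not counts of lost events. To be lost, an event must also be Grade 1 at entry (Grade 2 or higher is excluded), start after consent, worsen on treatment and stay as one record. The documents give no rate for any of these. Nor do they give a rate for other toxicities starting in screening.

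**The case against.** The strongest reply is that the text never says that a worsening AE is dropped. The 4.2.4.1 rule speaks of AEs occurring before the first infusion, does not mention worsening, and leaves room for exceptions stated elsewhere; 3.4.1 could be such an exception. The first part is right: a reader might infer an explicit instruction to discard every worsening event, and there is none. The second part does not carry. Section 3.4.1 defines a term and says nothing about which events enter the tables, and nothing in 4.2.4.1 makes an exception for worsening.

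Second, the single record is an inference. Protocol 6.4.1 counts deterioration of an existing condition during exposure as an AE, and protocol 6.4.3 has aggravated examination findings reported as AEs. If sites open a new record, the worsening is tabulated. This stands as a possibility. It also covers toxicity already present before consent, which is not an AE with onset in screening. But no text requires a new record when an ongoing AE worsens.

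Third, the pneumonitis route is narrow. Most onsets at the usual latency fall after the first dose and are tabulated under either reading, and sites are strongly encouraged to finish screening within 14 days. This stands.

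Fourth, safety is descriptive, extra summaries are allowed, and the listings and the deaths summary retain the events. That limits the harm, but a listing does not restore a missing count in a table by arm.

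**Conclusion.** The concern holds as a mismatch between a stated table rule and the SAP's own definition. Read literally, 4.2.4.1 and protocol 11.2.1 can leave an on-treatment worsening out of the all-AE, Grade 3 or higher, fatal-AE and AESI tables, in both arms. This requires that the AE starts between consent and first infusion and is kept as one record.

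The number affected cannot be derived. For pneumonitis it is about none with dosing by day 30 after radiation. With later dosing it is at most a small number of Grade 1 events, under the assumptions above. Other chemoradiation toxicities starting in screening are exposed too, to an unknown extent.

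Two stronger inferences are not supported. A reader might conclude that 5 to 14 MEDI4736 patients would have worsening pneumonitis removed from the tables; those figures count onsets before dosing if everyone starts at day 42, and assume nothing about worsening. A reader might also conclude that the drug's contribution to lung toxicity is understated. The rule applies to both arms, and the documents show no direction or size of effect on the difference. Nor would fatal cases disappear: they remain in the deaths summary, and only the separate table of AEs with outcome of death is exposed.

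**What to change.** In SAP 4.2.4.1, state that the AE summary tables include treatment-emergent AEs as defined in 3.4.1, so that an AE starting before the first infusion is excluded unless it worsens after the first dose. State also that a worsened AE is counted at its maximum grade after the first dose, with onset at the date of worsening. That date would come from the recorded grade changes or, where the site opened one, from the new AE record. The same onset rule should serve the AESI time-to-onset summaries. Align protocol 11.2.1.

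The cost is wording in two documents and minor programming, using grade-change data that the planned outputs already imply. AE counts would be slightly higher in both arms. Sample size, alpha and the efficacy analyses are untouched.

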3.4.6 Treatment exposure

Exposure will be defined as follows for the initial treatment period and for the re-treatment period:

Total (or intended) exposure of study medication,

- Total (or intended) exposure = $\min(\text{last dose date where dose} > 0\text{mg} + 13 \text{ days, date of death, date of DCO}) - \text{first dose date} + 1$

Actual exposure of MEDI4736/placebo

- Actual exposure = intended exposure – total duration of dose delays, where intended exposure will be calculated as above.

Dose reductions are not permitted per the CSP. The actual exposure calculation makes no adjustment for any dose reductions that may have occurred.

Calculation of duration of dose delays (for actual exposure):

- Since patients will receive 10 mg/kg via IV infusion q2w for up to 12 months (up to 26 doses), the duration of dose delays will be calculated as follows:

For all dosing dates:

Total duration of dose delays = Sum of (Date of the dose - Date of previous dose – 14 days)

Thus, if no delays were encountered, the duration would sum up to 0, since infusions were done every two weeks.

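### The SAP's adverse-event rate per 100 patient-years divides by drug exposure twice, and its event window can outlast the exposure time in its denominator (minor; descriptive output only)

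*SAP*

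**What the plan says.** SAP 4.2.4.1 makes the rate a firm output: "Each AE event rate (per 100 patient years) will also be summarised by preferred term within each SOC for the output summarising all AEs". It begins the definition with "the event rate is defined as the number of patients with that AE divided by the total drug exposure of patients" and continues "at risk of AE divided by the total drug exposure of patients and then multiplied by 365.25 x 100". The same section does not say which exposure measure is meant, or whether a patient's time stops at the first event.

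The main AE tables count "AEs observed up until 90 days following discontinuation of the study treatment (i.e., the last dose of randomised treatment", but stop earlier at "the initiation of the first subsequent anti-cancer therapy (including radiotherapy, with the exception of palliative radiotherapy" if that comes first. A second set ignores subsequent therapy: "all of the AE summaries will also be produced containing AEs observed up until 90 days following discontinuation of the study treatment".

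SAP 3.4.6 gives two exposure measures. Total (or intended) exposure runs from first dose to the earliest of last dose plus 13 days, death and data cut-off. Actual exposure subtracts dose delays. On periods it says: "Exposure will be defined as follows for the initial treatment period and for the re-treatment period". SAP 3.4 bases the main safety presentations on the initial 12-month treatment period. SAP 4.2.4 makes all safety summaries descriptive. Protocol 12.2.12 says only that AE rates per person-years at risk may be presented.

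**The concern.** There are two separate problems. First, a count divided twice by a number of days is not a rate per patient-year, whatever the scaling. The output cannot be produced in its stated unit without departing from the text.

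Second, deleting the repeated phrase does not settle the denominator. Events are collected over a longer span than the exposure that is summed, so the quotient overstates the rate per unit of time observed. The two sets of AE tables use different event windows over one exposure definition. The set that ignores subsequent therapy can therefore show higher rates for that reason alone. At stake is how readers interpret one descriptive safety output.

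**Working it through.** Neither document prints an AE rate, so there is no planned figure to reproduce. The check covers units, the two windows, and an illustration of size.

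**Units.** Let n be the patients with the AE and T the summed exposure in days.
- One division: n / T × 365.25 × 100 is patients per 100 patient-years.
- Two divisions: (n / T) / T has units of patients per day squared, and n / (T / T) has no time unit. Neither is the stated rate.

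**Windows (SAP 3.4.6 and 4.2.4.1).** Gap = 90 − 13 = 77 days. With k doses on the two-weekly schedule, exposure is 14(k − 1) + 14 = 14k days. The full AE window is 14(k − 1) + 91 = 14k + 77 days.

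| Doses | Exposure (days) | AE window (days) | Ratio |
|---|---|---|---|
| 1 | 14 | 91 | 6.50 |
| 6 | 84 | 161 | 1.92 |
| 13 | 182 | 259 | 1.42 |
| 26 | 364 | 441 | 1.21 |

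These are full-window ratios. Death, data cut-off or, in the main tables, early subsequent therapy narrows the gap. The relative effect is largest in patients who stop early.

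**Illustrative size.** These assumptions are not in the documents: dosing continues to exponential progression or 12 months, at the planning PFS medians in SAP 1.3 (10 months on placebo and 10 + 5 = 15 on MEDI4736), with a constant AE hazard μ on and off drug.
- λ = ln 2 / 10 or ln 2 / 15. Mean exposure = (1 − exp(−12λ)) / λ = 8.15 months (placebo) and 9.21 months (MEDI4736).
- g = 77 / 30.4375 = 2.53 months. For very rare AEs, inflation is 1 + g / mean exposure = 1.311 and 1.275.
- SAP 4.2.4.1 counts each patient once, so inflation falls as the AE becomes common. With L(μ) = λ/(λ+μ) × [1 − exp(−12(λ+μ))] + exp(−12(λ+μ)), inflation = [1 − exp(−μg)L(μ)] / [1 − L(μ)], where μ is set so that the numerator equals the stated percentage of patients.

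| Patients with the AE | Placebo | MEDI4736 |
|---|---|---|
| 5% | 1.304 | 1.269 |
| 20% | 1.284 | 1.250 |
| 40% | 1.254 | 1.220 |
| 60% | 1.217 | 1.185 |

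**Sensitivity, rare AEs (placebo, MEDI4736).**
- Off-drug hazard half the on-drug hazard: 1.155, 1.137. A quarter: 1.078, 1.069. None: no inflation.
- Only 30 extra days counted: 1.121, 1.107.
- A further 2% per month stopping for other reasons (mean exposure 7.36 and 8.28 months): 1.344, 1.306.
- Eight weeks of dosing past progression (9.13 and 9.95 months): 1.277, 1.254.

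**Arm comparison.** The window alone multiplies the MEDI4736-to-placebo rate ratio by 1.275 / 1.311 = 0.97 if the gap is 77 days in both arms. With 60 days on MEDI4736 and 40 on placebo it is 1.214 / 1.161 = 1.05.

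**The case against.** The strongest reply is that the double division is a slip with one workable reading. The repeated words look like a drafting duplicate, the scaling fits only one division, and a competent programmer would divide once. That stands. A reader might infer that the literal formula would bias the comparison of arms under 2:1 allocation, because the larger arm would be divided by its larger exposure twice. The documents do not support treating that as a real risk: the stated unit and scaling contradict the literal formula, so ratios computed from it describe nothing the plan intends.

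The window mismatch is less easily dismissed, but the objections to it carry weight. SAP 4.2.4.1 does not cite 3.4.6, so the 13-day endpoint is inferred. The wording matches total exposure, and using actual exposure would only shorten the denominator. The SAP openly names drug exposure as the denominator, and an exposure-adjusted rate is a legitimate choice if labelled as such. The main tables do not always run to 90 days. Percentages of patients by arm, which carry most of the AE reporting, are unaffected.

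What survives is that the text does not fix the denominator, that the natural reading mismatches it to the numerator, and that one exposure definition serves two event windows.

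**Conclusion.** The point holds as a minor correction. The formula needs one division removed, and the denominator needs a stated window. If drug exposure means total exposure in SAP 3.4.6, up to 77 days per patient can contribute events without time. In the illustration the full gap raises the patient-based rate by about 30% (placebo) and 27% (MEDI4736) for an AE in 5% of patients, 25% and 22% at 40%, and 22% and 18% at 60%. The effect is smaller if the hazard falls off drug or subsequent therapy starts early, and somewhat larger if exposure is shorter. All of this rests on the assumed hazard and dosing model.

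A reader might go further and infer that the safety comparison is biased for or against MEDI4736. The documents do not support that. The window effect on the arm ratio is small, roughly 0.97 to 1.05 in the cases tried, and its direction is not established. Only a descriptive rate is affected.

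**What to change.** Delete the second division and define: rate = patients with at least one event / total time at risk in days × 365.25 × 100.

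Time at risk should run from first dose of the initial treatment period to the end of the AE window used in that table. That is the earliest of:
- last dose of that period plus 90 days;
- death;
- withdrawal of consent or loss to follow-up (Protocol 5.9 ends study observation when consent is withdrawn);
- data cut-off;
- in the main tables only, first subsequent anti-cancer therapy other than palliative radiotherapy.

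State this for both sets of tables, and state whether time stops at the first event. Stopping there gives an incidence rate per person-years at risk, in line with Protocol 12.2.12, but it is a choice and not a necessary part of the correction.

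The cost is a short SAP definition and a small amount of programming; stopping at first event also needs a separate denominator for each preferred term. Reported rates will change. In the same model with the full window, compared with dividing once by exposure:
- If time does not stop at first event, every rate is multiplied by 8.15 / (8.15 + 2.53) = 0.76 on placebo and 9.21 / (9.21 + 2.53) = 0.78 on MEDI4736.
- If time stops at first event, the multipliers (placebo, MEDI4736) are 0.79 and 0.81 for an AE in 5% of patients, 1.02 and 1.03 at 40%, and 1.27 and 1.28 at 60%.
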